Data Safety and Monitoring Board (DSMB) The Data Safety and Monitoring Board will be charged with recommending changes in the study protocol or closure of the study if the incidence of falls or another adverse event in the intervention group at BVAMC is significantly greater than that observed in the control group at BVAMC. The board's membership will include a physician, a physical therapist and a nurse. The DSMB will meet quarterly either in-person or by conference call to discuss the study and any issues or concerns. Incidents will be reported to the DSMB by email.

The following incidents which occur at BVAMC will be reported to the DSMB and IRB immediately:

1. Falls by participants that occur during the inpatient portion of the study
2. Open wounds (Stage II or greater pressure ulcers indicating a breach of the skin's integrity) under the area of the StepWatch

The following incidents which occur at BVAMC will be reported to the DSMB quarterly:

1. Falls by participants that occur after the inpatient portion of the study, but while enrolled, together with statistics on the current fall rate at BVAMC
2. Participants' deaths that occur after the inpatient portion of the study, but while enrolled
3. Emergency department visits that occur after the inpatient portion of the study, but while enrolled
4. Rehospitalizations that occur after the inpatient portion of the study, but while enrolled
5. Participant transferred to ICU/CCU or Safe Harbor during the inpatient portion of the study
6. Participant dies during the inpatient portion of the study
7. Skin irritation in the immediate vicinity of the StepWatch

AEs, SAEs, and other incidents which involve UAB participants will be reported to the UAB IRB.

K. POTENTIAL BENEFITS: Assess the potential benefits to be gained by the individual subject, as well as benefits which may accrue to society in general as a result of the planned work.

For the group of patients who receive the hospital mobility intervention, it is expected they will maintain or improve their mobility to a greater degree than those in the usual care group. As ability to walk is a key component of all basic activities of daily living, the MP group may also experience an improvement in their ADL ability to a greater degree after hospital discharge. As mobility disability is associated with a reduction in quality of life, the MP group may experience an improvement in quality of life.

It is expected that there will be little direct benefit to those participants who are randomized to the control group. However, they will be visited three times a day for social visits, which may increase their feeling of wellbeing.

L. THE RISK-BENEFIT RATIO: This section should consist of the investigator's explanation of how he or she concluded that the risks to subjects are reasonable in relation to anticipated benefits, if any, to subjects, and the importance of the knowledge that may reasonably be expected to result.

The risks to the subjects are very small, whereas the results of this study will add substantively to what is currently known about how to improve outcomes due to low mobility for middle-aged and older adults who have a hospitalization. Functional decline, loss of mobility, and nursing home admission are well-recognized negative outcomes associated with hospitalization, and available evidence suggests low mobility to be a contributor to these adverse outcomes; determining the effectiveness of a hospital mobility program could have significant impact on functional decline and loss of mobility for hospitalized patients. The potential benefits are great if the study allows for the development of a hospital mobility program intervention that could ultimately decrease loss of mobility and functional decline and reduce ED visits, hospitalizations and the need for nursing home care after hospitalization.

References:

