**Figure 2: StepWatch****Figure 3: StepWatch data output**

(birresearch), accessible only by authorized study staff. No data will be stored in temporary files or on hard drives.

Randomization

Participants will be assigned to MP or UC using cluster randomization based on hospital ward at both the Birmingham VAMC and UAB Hospital. At study initiation, all five wards at the Birmingham VAMC will be assigned to the usual care group. Every 5 months a randomly chosen ward will shift from receipt of usual care to the mobility program (See Figure 4). At UAB Hospital, all four wards will be assigned to the usual care group at study initiation, which is expected to be at month 24 of the study. Every 3 months a randomly chosen study ward will shift from receipt of usual care to the mobility program (See Figure 4A). MP patients will receive three daily visits for progressive ambulation; the UC group will receive three daily “friendly visits.” Both groups will receive routine medical care as it is currently provided, including the provision of physical therapy if ordered by the physician.

Figure 4: Stepped Wedge Cluster Randomization with 5 VA Hospital Units. The order in which each unit receives the intervention is randomized, with staggered implementation. By conclusion of observation, all units have received the intervention. MP (grey bars) = Mobility Program initiated and continued on ward unit.

	Time (in months)						
Unit	1/18/17- 6/18/17	6/19/17 – 11/18/17	11/19/17 – 4/18/18	4/19/18 – 9/18/18	9/19/18 – 2/18/19	2/19/19 – 7/18/19	7/19/19 – 12/31/19
A	Control	MP					
B	Control		MP				
C	Control			MP			
D	Control				MP		
E	Control					MP	

Figure 4A: Stepped Wedge Cluster Randomization with 4 Hospital Units at UAB Hospital. The order in which each unit receives the intervention is randomized, with staggered implementation. By conclusion of observation, all units have received the intervention. MP (grey bars) = Mobility Program initiated and continued on ward unit.

	Time (in months)					
Unit	5/1/18 – 7/31/18	8/1/18 – 10/31/18	11/1/18 – 1/31/19	2/1/29 – 4/30/19	5/1/19 – 7/31/19	8/1/19 – 12/31/19
A	Control	MP				
B	Control		MP			
C	Control			MP		
D	Control				MP	

Daily visits

Mobility Program Group (MP):

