Our primary aim is to evaluate the impact of the mobility program on mobility in the year after hospital discharge using the UAB Life-Space Assessment (LSA). In our previous small VA-funded study of a mobility intervention, patients in the MP group had a mean LSA score that was approximately 10 points higher than in the UC group at four weeks' post-discharge. It is our expectation that the current study will replicate these results; specifically, that the 10-point difference will be apparent at 1-month post-discharge and persist thereafter. As described below, the primary statistical technique to address the primary aim will be mixed effects models. Assuming an exchangeable covariance structure across the repeated observations, a sample size of 190 participants provides greater than 90% power to detect a persistent 10-point difference in LSA scores at the $\alpha = .05$ level. We must also consider the reduced effective sample size due to clustering. It is a common practice to calculate the intraclass correlation (ICC) among clusters as a measure of how much more similar members of the same cluster are to each other than to the overall population. In this setting, we recognize that subjects at UAB may differ from subjects at the VA, leading to differences in the ICC. However, we still expect much more variability to come from individual patient factors than from the units. Using the data from our recently completed VA longitudinal study, we calculated an ICC for the LSA that rounded to 0; including data from UAB resulted in an ICC approximately 4 times larger. Assuming an ICC of 0.004 and subjects spread across 9 units, a sample size of 206 yields an effective sample size of 190 observations. In our recently completed VA longitudinal study during which patients were followed for 6 months after hospital discharge, 80% of the veterans completed at least 5 of the 6 monthly post-hospital assessments. We had 23 deaths and 3 withdrawals over the 6 months of follow-up among the 200 veterans in the study. Thus, in order to have an adequate (i.e. 206) sample size at 12-months, 258 patients will be enrolled allowing for patient losses due to

death or drop outs. Thus, while adding units from UAB to the study does increase the required sample size slightly due to the larger ICC, this is offset by the larger number of potential subjects that can be recruited.

Analytic Approach (for each specific aim)

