Descriptive statistics including mean, standard deviations, distribution, maximum and minimum values for the study variables will be calculated. Data will be examined graphically and by summary statistics for outliers and distributional properties (e.g., normality, skewness) that may lead to transformations or nonparametric analyses where indicated.

To analyze differences in LSA while accounting for changes in units over time, we will use a stepped-wedge design (Figure 4, above), a variation of cluster randomization in which each cluster is eventually assigned to intervention.²¹ By beginning with a pre-intervention period and implementing the interventions in ‘steps’ at set times, each unit serves as its own control, with pre-intervention observations used to estimate any underlying long-term or seasonal trends with precision so that effects from the intervention can be distinguished from these ‘secular’ trends. While the standard stepped-wedge design treats time in discrete blocks (the ‘steps’), this trial will be able to provide more robust estimates of secular trends because observations are linked to the date of each patient’s admission, providing a much finer temporal resolution. To understand the secular trends, we will start by examining smoothed plots of LSA over time overall and stratified by unit to identify especially large temporal fluctuations that may indicate unanticipated changes in processes or personnel. We will then model LSA during the time prior to the initiation of the intervention using mixed models,²² to account and test for heterogeneity among hospital units (in both means and trends) and possible nonlinearities. While secular trends must be accounted for in the final models, results from this preliminary analysis will inform whether potential trends can be considered to be linear, and whether all units can be considered to have the same trends over time.

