Informed by the modeling of secular trends, the final models will add in indicator terms for whether the observation occurred before or after the intervention, in addition to the appropriate modeling of secular trends. Additional more sophisticated modeling will evaluate the trends in the outcomes over time in the post-intervention periods to see whether temporal trends differ pre-and post- intervention. All statistical tests will be two-sided and will be considered to be significant if the associated p-value is <0.05. All analyses will be intention-to-treat based on the unit’s assignment at the time of a patient’s admission, and missing data will be imputed using a multiple imputation strategy, based on the characteristics of the data.

AIM 1: To test the effectiveness of a mobility program on recovery to pre-hospital mobility status or better and reduction of adverse outcomes in the year after hospitalization.

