To test the effectiveness of the intervention on mobility, LSA scores and changes in LSA scores for patients in the control condition will be compared to LSA scores from patients in the intervention condition. Mixed models will be used to examine and compare mean LSA over time with time considered a random effect. An indicator term will be included to denote whether the observation was from the period prior to or after implementation of the intervention. The indicator term will represent whether there was an overall difference in the LSA during the intervention period versus the pre-intervention period, and its statistical significance in the model for each outcome will be the primary test of whether the intervention had a significant effect on LSA. A priori we believe that an exchangeable covariance structure will be most suitable for the data. For the secondary hypotheses, i.e., self-reported outcomes for driving (yes/no) and ability to walk $\frac{1}{4}$ of a mile (yes/no), generalized linear mixed models (GLMMs) that account for repeated measures will be used to compare pre- and post-intervention periods. Given the randomized nature of the study design, adjustment for potential confounders will likely be unnecessary as they are expected to be equally distributed between the groups. However, as noted above, we will confirm that any potential confounders, e.g., age, length of hospitalization, and disease burden score (Cumulative Illness Rating Scale-Geriatrics, or CIRS-G²³) are indeed similar between the pre- and post-intervention periods and, should any not be, we will adjust for them in the statistical models provided they are not deemed to be consequences of the intervention.

To test the effectiveness of the intervention on adverse outcomes, we will use mixed models and GLMMs to model changes in functional decline (ADLs and IADLs), number of ED visits, and number of hospitalizations with an approach similar to the above. To test the effectiveness of the intervention on nursing home admission

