Impact of a Hospital Mobility Program on Function after Discharge

Statistical Analysis Plan

Sample Size Calculations: Our primary aim is to evaluate the impact of the mobility program on mobility in the year after hospital discharge. In our previous small VA-funded study of a mobility intervention, patients in the MP group had a mean LSA score that was approximately 10 points higher than in the UC group at four weeks post-discharge. It is our expectation that the current study will replicate these results; specifically that the 10 point difference will be apparent at 1-month post-discharge and persist thereafter. As described below, the primary statistical technique to address the primary aim will be mixed effects models. Assuming an exchangeable covariance structure across the repeated observations, a sample size of 190 participants provides greater than 90% power to detect a persistent 10-point difference in LSA scores at the $\alpha = .05$ level. We must also consider the reduced effective sample size due to clustering. It is a common practice to calculate the intraclass correlation (ICC) among clusters as a measure of how much more similar members of the same cluster are to each other than to the overall population. In this setting, we expect much more variability to come from individual patient factors than from the units. Using the data from our recently completed VA longitudinal study, we calculated an ICC for the LSA that rounded to 0. Assuming a larger ICC of 0.001 and subjects spread across 5 units, a sample size of 198 yields an effective sample size of 190 observations. In our recently completed VA longitudinal study during which patients were followed for 6 months after hospital discharge, 80% of the veterans completed at least 5 of the 6 monthly post-hospital assessments. We had 23 deaths and 3 withdrawals over the 6 months of follow-up among the 200 veterans in the study. Thus, in order to have an adequate (i.e. 198) sample size at 12-months, 226 patients will be enrolled allowing for patient losses due to death or drop outs.

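### The sample size leaves out the secular-trend adjustment that the primary model requires, so 206 patients do not carry the information of 190 and power above 90% is unsupported

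*Protocol*

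**What the plan says.** The protocol (section E, Sample Size Calculations) sizes the trial in three steps.

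1. It states that "a sample size of 190 participants provides greater than 90% power to detect a persistent 10-point difference in LSA scores".
2. It allows for clustering: with an ICC of 0.004 and 9 units, "a sample size of 206 yields an effective sample size of 190 observations".
3. It raises 206 to 258 for losses.

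The SAP (Sample Size Calculations) takes the same route with 5 units and an ICC of 0.001: "a sample size of 198 yields an effective sample size of 190 observations". Neither document has a step for calendar time.

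The analysis sections describe a model that needs one. The protocol's Analytic Approach says "While secular trends must be accounted for in the final models" and adds the before/after indicator "in addition to the appropriate modeling of secular trends". Under AIM 1, of that indicator, "its statistical significance in the model for each outcome will be the primary test of whether the intervention had a significant effect on LSA". The SAP repeats these statements.

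Under Randomization, all wards begin on usual care. At the VA, "Every 5 months a randomly chosen ward will shift from receipt of usual care to the mobility program" (Figure 4). UAB follows the same pattern at 3-month intervals (Figure 4A).

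**The concern.** The design effect used is the one for a parallel cluster trial, in which both arms run side by side and treatment is unrelated to calendar time. Here early observations are mostly usual care and late ones mostly mobility program. Once the model adjusts for trend, only the part of the treatment contrast not explained by time informs the estimate. The sample-size text therefore describes a more precise test than the one planned.

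The power statement is the justification for 258 patients and the yardstick for a null result. As written, it implies less than a 10% chance of missing a true 10-point LSA difference.

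**Working it through.** **The plan's own figures.** Design effect = 1 + (m - 1) × ICC, where m is patients per ward.
- Protocol: 1 + (206/9 - 1) × 0.004 = 1.0876; 206/1.0876 = 189.4.
- SAP: 1 + (198/5 - 1) × 0.001 = 1.0386; 198/1.0386 = 190.6.
- Enrolment: 206/0.80 = 257.5, so 258.

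All three reproduce. The formula was applied correctly; it does not fit the planned test.

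**Inputs.** From the documents: the Figure 4 dates (5 VA wards, 1/18/17 to 12/31/19); the Figure 4A dates (4 UAB wards, 5/1/18 to 12/31/19, reading 2/1/29 as 2/1/19); ICC 0.004; 206 evaluable patients; two-sided alpha 0.05. Assumed, because not stated: even recruitment, a random ward intercept, and a VA:UAB split by ward-days, 5:4 or 80:20.

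**Hand check.** Under these splits the correlation r between mobility-program status and calendar time is 0.658 to 0.684. A linear trend alone inflates the variance by 1/(1 - r²): 1/(1 - 0.433) = 1.76 to 1/(1 - 0.468) = 1.88.

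**Full calculation.** The generalised-least-squares variance V of the intervention coefficient was computed on daily ward cells with total variance 1. It was compared with 4/190, the variance for 190 independent patients split 1:1. Ratio R = V/(4/190); effective N = 190/R.

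| Time terms in the model | R | Effective N |
|---|---|---|
| None | 0.96-0.97 | about 197 |
| Common linear trend | 1.74-1.84 | 103-109 |
| Hospital + linear trend | 1.92-1.96 | 97-99 |
| Hospital-specific linear trends | 2.04-2.08 | 91-93 |
| Hospital-specific discrete steps | 2.18-2.26 | 84-87 |
| SAP version (198, 5 wards, ICC 0.001), none | 0.99 | 192 |
| SAP version, linear trend | 2.04 | 93 |

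Without a time term the method comes close to the plan's figure, so the trend adjustment makes the difference. Moving the ICC from 0 to 0.02 moves the common-linear ratio only from 1.69 to 1.99.

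**Power.** Power = Φ((1.96 + z)/√R - 1.96), where z is the normal quantile of the nominal power at 190. For nominal 90% (z = 1.2816) and R = 1.74: 3.2416/1.319 - 1.96 = 0.50, giving 69%. For R = 2.08: 3.2416/1.442 - 1.96 = 0.29, giving 61%. The detectable difference at 90% power is 10 × √R × 3.2416/(1.96 + z).

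| Nominal power at 190 | Implied SD of patient-average LSA | Power, continuous trends | Power, discrete steps | Detectable difference (points), continuous trends |
|---|---|---|---|---|
| 90% | 21.3 | 61-69% | 58-59% | 13.2-14.4 |
| 95% | 19.1 | 71-78% | 67-68% | 11.8-13.0 |
| 99% | 16.1 | 84-90% | 81-83% | 10.0-10.9 |

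Implied SD = 10/((1.96 + z) × √(4/190)). To deliver 90%, nominal power would have to be Φ(3.2416 × √R - 1.96): 99.0% at R = 1.74 and 99.7% at R = 2.08. The SAP version with a linear trend gives 62%, 71% and 85%.

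**Calendar.** The protocol text puts the UAB start at a time "which is expected to be at month 24 of the study", about 1/18/19 if month counting begins on 1/18/17. Figure 4A starts at about month 16.
- Moving the UAB schedule intact to month 24 leaves the hospital-adjusted linear ratios at 1.92-2.08 and lowers the common-trend ratio to 1.39-1.55 (N 123-136).
- Also stopping it at 12/31/19 gives 1.63-1.87 with a hospital term and 1.09-1.29 without (N 147-174), but the fourth UAB ward would then never switch.

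**Recruitment pattern.** On the figures' dates, front-loaded or back-loaded recruitment widens the range to 1.56-2.51. The month-24 start with front-loading and a common trend gives as little as 1.22.

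**Attrition (minor).** The 20% allowance at 12 months rests on 6-month data, in which (23 + 3)/200 = 13% were lost. If that rate stayed constant, which is an assumption, 0.87² = 0.757 and 258 × 0.757 = 195 would remain at 12 months, not 206.

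**The case against.** The best case for the plan has five parts.

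- **The stated arithmetic is correct, and the figure is offered only as a correction for clustering.** True. The fault is a missing design component, not a slip in calculation. The 190 is still the only effective size given for the primary test, and for that test it is wrong.
- **No shortfall in power is proved.** Also true. Power above 90% has no upper limit, and without an SD or within-patient correlation every power figure here is conditional. The ratios and effective sizes are not affected by this.
- **The size depends on the calendar and on trend terms that the plan leaves open.** This stands. Ratios of 1.92 and above need hospital terms that the plan does not specify, and the month-24 start with a common trend gives lower values.
- **206 may be too few, because a mixed model also uses partial follow-up.** This stands in part. If all 258 contributed fully, power under continuous trends would be 71-78%, 80-86% or 91-95% at nominal 90%, 95% or 99%, and delivering 90% would still need nominal power of 96.9-98.7%. Only the lowest calendar case could then reach 190 (147-174 × 258/206 = 184-218), and that case leaves one UAB ward unswitched. By the same argument, the 195 counts patients present at month 12, not information.
- **The protocol is dated after the planned end of recruitment, and the final confidence interval will reflect the trend anyway.** The estimate and its standard error are indeed unaffected. The stated power remains the figure against which a null result would be read.

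Using admission dates rather than discrete steps does not remove the problem: the linear-trend ratios above already use daily dates. Adjusting for baseline LSA would lower the absolute variance but leave the ratio essentially unchanged.

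**Conclusion.** The concern holds. The conversions of 206 and 198 patients to 190 are wrong as effective sizes for the trend-adjusted primary test. On the Figure 4 and 4A dates, with even recruitment and a random ward intercept, the variance is about 1.7 to 2.3 times what the plan allows for. At 206 evaluable patients, no calendar or trend model tested, including the month-24 variants, reaches 190.

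Power above 90% is unsupported, not disproved. With continuous trends on the figures' dates, the chance of missing a true 10-point difference is 31-39%, 22-29% or 10-16% at nominal 90%, 95% or 99%. The documents give nothing to show nominal power of 99.0% or more.

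**What to change.** In both documents, replace the statements that 206 or 198 patients yield 190. First reconcile the UAB start (month 24 in the text, 5/1/18 in Figure 4A). Then:

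- Recompute effective size, power and the LSA difference detectable with 90% power from the stepped-wedge variance, using the actual two-hospital schedule, a ward random effect, and the calendar-time and hospital terms of the final model.
- Give results for a linear and a more flexible trend, because the Analytic Approach leaves the form open.
- State the LSA SD, within-patient correlation, nominal power at 190 and 12-month attrition assumed.
- Keep enrolment at 258.

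The cost is a short calculation and some rewording. The stated power becomes explicit, conditional and less favourable. No patients are added and the analysis does not change.

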Confidentiality: To help protect confidentiality, participants will be interviewed in their ward rooms with the door closed or the curtain pulled; telephone assessments will be conducted from private offices with the doors closed. To help protect privacy, participants will be provided with appropriate gown coverage if they walk in the hallways during study walking sessions.

For Birmingham VAMC veterans, data will be collected using paper records; while on the wards, these will be physically present with study staff at all times. Paper records will be stored in locked file cabinets behind locked doors in study staff offices in the BVAMC, rooms 8211, 8223, 8224 and 8218. As with the paper records, active StepWatches will be physically present with study staff at all times (when not worn by the participant). No hard-copy data will be removed from the VA protected environment, nor will any PHI be transmitted electronically.

Data will be entered by study staff into MS Office applications under VA license, and will be stored on the secure research server (birresearch) in a secure folder to which only study staff will have access. StepWatch data will likewise be stored in this secure folder. No study data will be stored in temporary files or on a computer hard drive. Information from this study will only be reported in aggregate for research purposes without the possibility of identifying individuals in the study. Data retention and data destruction will follow current regulations.

The PI will have ultimate responsibility for the security of the data. Study staff will contact the PI and study coordinator immediately in the case of any suspected or confirmed theft, loss, or unauthorized access of data, or of non-compliance with security controls. The PI or study coordinator will report incidents to the PO and ISO by phone and/or email, and to the National Service Desk by submitting a ticket via phone, email, or online ticket submission system [see VHA Handbook 1200.05 ¶10j, VHA Handbook 1058.01 ¶11.a, VA Handbook 6500, Appendix D, and VHA Handbook 6500.2].

Study personnel who leave the research team will have their access to the secure folder terminated and will turn in all keys to offices and file cabinets upon leaving the team.

UAB participants' data will be stored in UAB facilities per UAB guidelines. This data will be de-identified and combined with de-identified data from VA participants for the purposes of conducting analysis.

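### The SAP still sizes a one-hospital trial, and neither document states a hospital effect for the two separately randomised wedges that are pooled

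*Protocol*

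**What the plan says.** **Design.** Under Randomization, the protocol assigns wards in two wedges. Figure 4 has five VA wards crossing over at 5-month steps from 1/18/17. Figure 4A has four UAB units crossing over at 3-month steps from 5/1/18. The text of the same section gives the UAB start differently: "which is expected to be at month 24 of the study". Under J. Protection of Subject, UAB data are to be "combined with de-identified data from VA participants for the purposes of conducting analysis".

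**Sample size.** The protocol states "we recognize that subjects at UAB may differ from subjects at the VA", and uses this to raise the ICC: "Assuming an ICC of 0.004 and subjects spread across 9 units", with 206 analysed and 258 enrolled. The SAP's Sample Size Calculations has 5 units, ICC 0.001, 198 analysed and 226 enrolled, and the SAP does not name UAB as a site.

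**Analysis.** The Analytic Approach, in nearly the same words in both documents, says that "each unit serves as its own control" and plans a preliminary model of pre-intervention data "to account and test for heterogeneity among hospital units (in both means and trends) and possible nonlinearities". Informed by that step, "the final models will add in indicator terms for whether the observation occurred before or after the intervention", together with suitable modelling of secular trends. Aim 1 makes the indicator the primary test, treats time as a random effect and expects an exchangeable covariance. On the outcome, it says "LSA scores and changes in LSA scores for patients in the control condition will be compared". No hospital effect is stated, nor whether a unit effect is fixed or random.

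**The concern.** The two documents size different trials, so the SAP cannot serve as the plan for the one being run.

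On the model, wards were randomised within hospital. On 5/1/18 three of the five VA wards (A, B and C in Figure 4) are already on the mobility program, while all four UAB units are on usual care. At a given calendar date, treatment is therefore related to hospital. If the model fits one calendar trend to both hospitals and does not condition on hospital, part of the treatment coefficient is a non-randomised VA-UAB contrast. The protocol itself expects that the patients may differ. The choice of term currently rests on a preliminary look at the data.

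**Working it through.** **1. Reproduce the stated sizes.** Design effect = 1 + (m - 1) x ICC, with m = patients per unit.

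| | Protocol | SAP |
|---|---|---|
| m | 206/9 = 22.9 | 198/5 = 39.6 |
| Design effect | 1 + 21.9 x 0.004 = 1.088 | 1 + 38.6 x 0.001 = 1.039 |
| Effective N (both state 190) | 206/1.088 = 189.4 | 198/1.039 = 190.6 |
| Implied loss | 1 - 206/258 = 20.2% | 1 - 198/226 = 12.4% |

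Each document is consistent within itself. Both cite the same two loss figures from the prior study: 80% completed at least 5 of 6 assessments (20% did not), and 23 + 3 = 26 of 200 died or withdrew (13%). The protocol's allowance matches the first (206/0.80 = 257.5, so 258). The SAP's is close to the second (198/0.87 = 228, against 226).

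**2. UAB start.** From 1/18/17 to 5/1/18 is 468 days, or 15.4 months, not 24.

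**3. Shift of the treatment estimate.** Generalised least squares on the Figure 4 and 4A dates (the Figure 4A entry 2/1/29 read as 2/1/19), with a ward random intercept at ICC 0.004 and 206 patients. Accrual by ward is not given; I assume it uniform in time, with a UAB share of 30%, 44% or 50%. A 1-point UAB-minus-VA level difference is projected onto the treatment coefficient.

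| Model | Shift per 1-point gap (UAB share 30%, 44%, 50%) |
|---|---|
| Common linear trend, no hospital effect | -0.324, -0.376, -0.386 |
| Common calendar steps, no hospital effect | -0.309, -0.331, -0.328 |
| No time trend, no hospital effect | about +0.04 |
| Hospital effect, or fixed ward effects | 0 |

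**4. Size of the gap.** The documents do not split the ICC. Assume that 0.003 to 0.004 of it lies between hospitals. With 5 and 4 wards, the between-ward variance due to a gap is gap² x (5/9)(4/9) = gap² x 20/81. So gap/SD = sqrt(0.003/(20/81)) = 0.110 to sqrt(0.004/(20/81)) = 0.127.

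No SD is given. A two-sample comparison of 95 v 95 with exactly 90% power for 10 points implies SD = 10/((1.960 + 1.282) x sqrt(2/95)) = 21.3, read as the SD of a patient's mean LSA. Because the plan claims more than 90%, 21.3 is an upper bound on this reading. The gap is then 2.3 to 2.7 points.

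**5. Bias.** Lowest: 0.309 x 2.35 = 0.73 points. Highest: 0.386 x 2.71 = 1.05 points. Under the linear trend the bias is 0.18 to 0.26 SE, and two-sided type I error is 5.4% to 5.8%. If the ICC refers instead to single visits, and eight visits are averaged with an assumed correlation of 0.5 to 0.7, the bias is 0.9 to 1.3 points.

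**6. Price of the hospital effect** (linear trend, SD 21.3, 206 patients).

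| | Random ward only | Hospital effect + random ward |
|---|---|---|
| SE | 4.06 to 4.13 | 4.29 to 4.30 |
| Power for 10 points | 68% to 69% | about 64% |
| Mean squared error at the gap in step 4 | 17.3 to 17.8 | 18.4 to 18.5 |

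The variance ratio is 1.086 to 1.116. Break-even gap = sqrt(extra variance)/|shift| = 3.6 to 3.7 points.

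**The case against.** The strongest reply is that the modelling point is under-specification, not error. The plan treats each unit as its own control, says it will account for unit heterogeneity in means and trends, and offers its confounder list only as examples. That stands: a reader might infer that unit effects will be dropped, and nothing in either document says so. However, a random ward intercept at the protocol's own ICC removes little of the shift, so implied unit effects do not settle the matter. A change-from-baseline outcome would cancel a stable gap, but Aim 1 names both scores and changes.

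The shift also depends on the trend model. Aim 1's random time effect is ambiguous. If it means calendar time, random quarterly effects carrying 0.1% to 5% of the variance give a shift of only about -0.06 to +0.04. It may equally mean follow-up time, and the Analytic Approach requires secular trends to be modelled, so a fixed common trend is plausible but not the only reading.

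The hospital effect does not lower mean squared error at the gap worked out above. That stands too, and is why the case rests on validity.

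Two stronger inferences fail. A reader might conclude from the SAP that too few patients will be enrolled; the protocol gives 258 in all three places where it states enrolment. A reader might also conclude that the trial has only about 64% power. That figure rests on an upper-bound SD, and most of the fall from 90% comes from the stepped-wedge layout with trend adjustment, a separate matter from the hospital effect.

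**Conclusion.** The SAP's sample size and site description are wrong for the two-hospital trial. This needs no assumption and should be fixed. The UAB start date is an inconsistency within the protocol; I attach no bias to it.

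The missing hospital effect is a cheap improvement. The possible bias is small, about a tenth of the target difference at most in the main calculation. It is of unknown sign, because the documents do not say which hospital has the higher LSA. It rests on an assumed SD, accrual split and ICC split, and on a common fixed calendar trend. The documents do not support saying that the primary result will be confounded. They support saying that the primary model should condition on the stratum within which wards were randomised, by a rule fixed in advance.

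**What to change.** **SAP.** Update to 9 units, ICC 0.004, 206 analysed and 258 enrolled; state one loss allowance and the prior-study figure that it comes from; name UAB as a site. Reconcile the two UAB start dates in the protocol's Randomization section. Cost: wording only.

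**Both documents.** Include a fixed hospital effect plus a random ward intercept in the primary mixed model, whatever the preliminary heterogeneity test shows, and carry the hospital effect into the GLMM and Cox models. Keep hospital-specific calendar trends as a sensitivity analysis: they cost about 15% to 33% more variance, and the documents give no evidence that trends differ. Fixed ward effects would also remove the shift, but at about 50% more variance, so they are not proposed as primary.

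The named downside of the hospital effect is the 9% to 12% rise in variance, with no gain in mean squared error unless the hospital gap exceeds about 3.6 points. No new data are needed. Figures 4 and 4A end on 12/31/19 and the protocol is dated February 5, 2021, so the change comes after planned accrual. Make it as a dated amendment before outcomes are compared by group.
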